1.1.1.5 Clinical Activity

In the placebo-controlled Phase 3 study XL184-301 in 330 MTC subjects, a significant increase in median PFS was seen in the cabozantinib arm compared with placebo (11.2 vs 4.0 months; hazard ratio [HR] =0.28; 95 CIs: 0.19, 0.40). Confirmed PRs occurred in 28% of cabozantinib-treated subjects and none in the placebo arm; responses were durable (median duration 14.6 months)²⁶. An unplanned administrative analysis of overall survival (OS) performed at the request of the FDA with a data cut-off of 15 June 2012 (75% of required deaths) showed a trend for improved duration of OS in the cabozantinib arm compared with placebo (26.0 months vs 20.3 months; HR = 0.83; 95% CI: 0.60, 1.14). In the Phase 1 Study XL184-001, with an enriched MTC population, PRs were reported in 29% of 35 MTC subjects with measurable disease across all dose levels and in 28% of 25 MTC subjects treated at the MTD. The median duration of treatment for the subjects in Study XL184-001 with PRs was 17.7 months with one subject receiving treatment for 68.4 months on XL184-001 before rolling over onto maintenance trial XL184-900 to continue to receive cabozantinib²⁵.

In addition to MTC, cabozantinib has demonstrated findings consistent with broad clinical anti-tumor activity in early Phase 1 and Phase 2 studies in several other tumor

types. In a randomized discontinuation trial (RDT) XL184-203, the following disease control rates (DCR = complete response [CR] + partial response [PR] + stable disease [SD]) at Week 12 were observed in tumor types including non-small cell lung cancer (NSCLC), 38%; breast cancer, 48%; melanoma, 46%; ovarian cancer, 53%; hepatocellular carcinoma (HCC), 66%; and CRPC, 66%. In Study XL184-008, clinical activity was also observed in differentiated thyroid cancer (DTC; DCR = 73% at 24 weeks) and renal cell carcinoma (RCC; median progression-free survival [PFS] = 12.9 months). Observations of clinical activity have included decrease of soft tissue tumor lesions including visceral metastases, effects on metastatic lesions on bone scan (partial or complete bone scan resolution), reduction in serum markers of bone resorption and formation, reduction in circulating tumor cells (CTCs) in subjects with prostate cancer with increases in hemoglobin, and improvements in bone pain and reductions in narcotic use in subjects with bone metastases (Investigator Brochure, Version 9, 2013).

In the Phase 2 study XL184-203, cabozantinib demonstrated broad clinical activity in men with CRPC (Smith et al. 2013). During the RDT phase, the majority of CRPC subjects with bone metastases and elevated total alkaline phosphatase (t-ALP) levels at baseline showed reductions in t-ALP²⁶. Similarly, during the non-randomized expansion (NRE) phase, the majority of CRPC subjects at the 100 mg assigned dose showed reductions in circulating bone specific alkaline phosphatase (BSAP)²⁷. These effects were independent of prior or concomitant bisphosphonate treatment. Reductions in bone biomarkers were also evident in the 40 mg CRPC NRE cohort (Investigator Brochure, Version 9, 2013). Effects on bone scan were assessed by an independent reader, and pain and narcotic use were prospectively assessed using an interactive voice recording system (IVRS) and a diary. Subjects achieved a bone scan response (BSR) in both the 100 mg and 40 mg assigned NRE dose cohorts (67% and 49%, respectively). Among subjects with baseline pain of at least 4 (0-10 scale by Brief Pain Inventory [BPI]), a majority had at least a decrease of 30% in the average daily worst pain compared with baseline in both cohorts (100 mg: 64% of subjects; 40 mg: 69% of subjects). In addition, more than half of subjects decreased narcotic use (Investigator Brochure, Version 9, 2013).

1.1.1.6 Translational Medicine

RET mutations

Of the 36 subjects tested in the XL 184-001 study, 67% were found to harbor *RET* mutations in either blood or tumor samples. Of the remaining 12 subjects, three (8%) of the subjects showed no evidence of *RET* mutation in either tumor or blood samples, and 9 (25%) subjects had inadequate data. These results confirmed the high rate of *RET* mutations associated with this disease. Of the three subjects showing no evidence of *RET* mutation in either tumor or blood samples, two achieved PR (one confirmed) and one showed PD as best response, indicating that mutations in *RET* may not be necessary for clinical benefit from treatment with cabozantinib.

Serial skin biopsies from a patient with MTC enrolled in the expanded MTD (eMTD) Cohort and were analyzed using fluorescence-based IHC. Levels of phosphorylated targets of cabozantinib, MET, RET, and KIT, were significantly decreased (40%, 40%, and 61%, respectively). In addition, decreases in key downstream mediators of cabozantinib target receptors were also measured; pERK and pAKT showed decreases of 55% and 39%, respectively. These effects are similar to those observed inpreclinical experiments²⁸, indicating that exposure to cabozantinib results in consistent changes in target signaling pathways.

In the study XL 184-301 (EXAM trial), archival tumor samples to determine *RET* mutational status in tumors and a whole blood sample to determine hereditary *RET* status were collected. *RET* status was determined in 65% (215/330) of the enrolled subjects. Of these 215 subjects, 79% had activating *RET* mutations and 21% had no *RET* mutations detected. Of 85 evaluated subjects with either no *RET* mutations or unknown RET status, 16 were found to have a *RAS* gene mutation. Cabozantinib had activity across all *RET* and *RAS* mutational subgroups, and demonstrated response rates of 22-32%, consistent with the response rate of subjects in the study overall. Subjects with *RET* mutations had significantly longer median PFS (60 weeks) than subjects who were *RET* mutationnegative (25 weeks). Subjects with *RAS* mutations had a median PFS of 47 weeks, indicating that clinical activity measured in the *RET* mutation-negative subgroup can be attributed partially to subjects with *RAS* mutations (Investigator Brochure, Version 9, 2013).

BRAF

Preliminary analysis of 48 melanoma subjects with both tumor response and BRAF mutation data suggests that the clinical activity of cabozantinib is independent of BRAF mutation status(Investigator Brochure, Version 9, 2013).. Clinical activity of

cabozantinib also appears to be independent of epidermal growth factor receptor (EGFR) and KRAS mutation status in NSCLC subjects based on the preliminary data (Investigator Brochure, Version 9, 2013).

Biomarkers of response of anti-angiogenic therapies

Plasma samples from patients with GB (XL-184-201) were analyzed for several biomarkers of response to anti-angiogenic agents, including levels of VEGF-A, sVEGFR2, and PlGF. Changes in pharmacodynamic markers consistent with cabozantinib on-target effects were observed after cabozantinib administration in 40 subjects treated with a starting dose of 140 mg FBE weight (175 mg malate salt weight). Changes in PlGF (↑), VEGF-A (↑), sVEGFR2 (↓), and soluble KIT (sKIT)(↓) reached statistical significance at multiple time points, particularly Days 15 and 29. Soluble MET as a potential biomarker of MET inhibition was modulated (↑) upon cabozantinib treatment and changes reached statistical significance as well, on Day 15 and Day 57 (Cycle 3 Day 1) (Investigator Brochure, Version 9, 2013).

In the study XL 184-301 (EXAM trial), exposure to cabozantinib resulted in significant decreases in the levels of the circulating sVEGFR2 and sKIT, consistent with results observed in other cabozantinib studies and with other anti-VEGFR2 inhibitors, and a modest but statistically significant relationship between plasma cabozantinib exposure and pharmacodynamic response was apparent (Investigator Brochure, Version 9, 2013).

Markers of bone turnover

Circulating CTx was reduced in the majority of CRPC patients included in the XL-184-203 study²⁶. Similar changes were seen in NTx. These effects of cabozantinib on circulating CTx and NTx levels appear to be independent of prior or concomitant bisphosphonate treatment or presence of bone metastases²⁷. Consistent with effects of cabozantinib on osteoblast activity, the majority of CRPC RDTsubjects with bone metastases and elevated t-ALP levels at baseline showed reductions in t-ALP (Investigator Brochure, Version 9, 2013). Similarly, the majority of CRPC NRE subjects at the 100 mg assigned dose showed reductions in circulating BSAP²⁶. These effects were independent of prior or concomitant bisphosphonate treatment. Reductions in bone biomarkers were also evident in the 40 mg CRPC NRE cohort: the median change in CTx at Week 12 was a 31% reduction and 50% of evaluable patients exhibited a decrease in BSAP at week 12 or later (Investigator Brochure, Version 9, 2013).

Circulating tumor cells

In metastatic prostate cancer, CTC counts at baseline have prognostic value, and changes on therapy have been considered to be predictive of treatment benefit²⁹. For the 100 mg CRPC NRE cohort, robust reductions in CTCs were observed regardless of prior therapy in 62 subjects with baseline CTC counts $\geq 5/7.5$ mL of blood and a Week 6 and/or Week 12 assessment. Fifty-seven subjects (92%) had $\geq 30\%$ decrease in their CTC count, while 39% of evaluable subjects converted to < 5 CTCs at Week 6^{27} . Similarly, for the 40 mg CRPC NRE cohort, reductions in CTCs were observed regardless of prior therapy in 39 subjects with baseline CTC counts $\geq 5/7.5$ mL of blood and a Week 6 and/or Week 12 assessment: 67% demonstrated CTC decrease $\geq 30\%$ in their CTC count, while 22% of evaluable subjects converted to < 5 CTCs at Week 6 (Investigator Brochure, Version 9, 2013).

1.3 Study Population,

1.3.1 Study Population for the Study:

Patients with malignant PHs and PGs have metastases into visceral organs and/or the skeleton. Depending on metastases location, the patients can be classified as follows:

40% of the patients have only visceral involvement (liver, lungs, lymph nodules)

40% have visceral and bone metastases

20% have bone metastases only.

Based on this information, we will divide our study population in two different branches:

- Main branch: 14 patients with measurable disease (+/- bone metastases)
- Exploratory branch: 8 patients with bone metastases only (+/- small non-measurable lesions).

2 STUDY OBJECTIVES AND DESIGN

2.1 Study Objectives

The objectives of this study are as follows:

Primary Endpoint (14 patients with measurable disease)

To estimate best overall response rate by RECIST 1.1¹³ in patients with measurable disease determined by a. CT or b. MRI

Secondary Endpoints (All patients)

- 1. To estimate progression-free survival at 1-year
- 2. To correlate blood pressure control and change/discontinuation of antihypertensive medications with tumor responses
- 3. To correlate symptomatology evaluation by the MD Anderson symptom Inventory (MDASI) with tumor responses
- 4. To correlate plasma metanephrines and chromogranin A with tumor responses
- 5. To correlate plasma C-reactive protein and interleukin-6 with symptoms and tumor responses
- 6. Toxicity assessment by the Common Terminology Criteria for Adverse Events (CTCAE)
- 7. To correlate both c-MET expression by IHC as well as MET amplification by FISH in archived samples and correlate these biomarkers with overall prognosis and responsiveness to cabozantinib.

Exploratory Endpoints (For patients with only bone metastases)

- 1. Best overall response rate in patients with bone metastases only (8 patients) as determined by FDG-PET/CT
- 2. FDG-PET/CT SUV_{max}, advanced volumetric measures including SUV_{peak}, metabolic tumor volume (MTV), and total lesion glycolysis (TLG)
- 3. Time to skeletal related events
- 4. Incidence of skeletal related events at 4 months and one year
- 5. Markers of bone turnover (bone specific alkaline phosphatase and CTx)

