The skeleton is involved in 80% of patients with malignant PHs and PGs⁴. In 20% of these patients, the skeleton is the only location of metastatic spread⁴. Bone metastases are usually lytic and blastic, expansile, and associated with increased morbidity and decreased overall survival⁴. Up to eighty percent of patients with bone metastases develop skeletal related events (SREs) such as: bone pain, fractures, and cord compression that need radiation therapy and/or surgery⁴. Patients experience SREs rapidly once bone metastases are developed (median 4.4 months)⁴. Fifty percent of patients who develop an SRE develop a second SRE within a median of 10 months⁴. Palliative radiation therapy and surgery are frequently required to improve pain and release cord compression. Molecular targeted therapies and chemotherapy may prevent SREs⁴.

Experience with molecular targeted therapies

A recently published retrospective intention-to-treat study described potential clinical benefits derived from sunitinib in patients with metastatic PHs and PGs⁷. Seventeen patients with progressive disease over a period of 6 months were treated with 37.5-50 mg of sunitinib daily, 4 weeks on, 2 weeks off. Patients were followed with radiographic and biochemical studies every 2 to 3 months. As per RECIST 1.1, 8 patients (47%) exhibited clinical benefits: 3 patients had partial responses and 5 had prolonged stabilization of disease, including 4 patients with extensive skeletal metastases (but not other metastases) identified by ¹⁸F-FDG-PET/CT scan. The tumors that responded to treatment also exhibited more than 30% reduction in glucose uptake 2-3 months after initiation of treatment compared with baseline. Patients who experienced partial response or prolonged stabilization of disease improved blood pressure and some discontinued treatment with antihypertensive medications. Most patients who benefited from sunitinib carried *SDHB* mutations. Unfortunately, most patients who experienced clinical benefits later developed tumor progression⁷.

Hypothesis

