- 4. To correlate plasma metanephrines and chromogranin A with tumor responses
- 5. To correlate plasma C-reactive protein and interleukin-6 with symptoms and tumor responses
- 6. Toxicity assessment by the Common Terminology Criteria for Adverse Events (CTCAE)
- 7. To correlate both c-MET expression by IHC as well as MET amplification by FISH in archived samples and correlate these biomarkers with overall prognosis and responsiveness to cabozantinib.

Exploratory Endpoints (For patients with only bone metastases n=8)

- 1. Best overall response rate in patients with bone metastases only (8 patients) as determined by FDG-PET/CT
- 2. FDG-PET/CT SUV_{max}, advanced volumetric measures including SUV_{peak}, metabolic tumor volume (MTV), and total lesion glycolysis (TLG)
- 3. Time to skeletal related events
- 4. Incidence of skeletal related events at 4 months and one year
- 5. Markers of bone turnover (bone specific alkaline phosphatase and CTx)

STUDY DESIGN

This is a prospective phase II study

NUMBER OF SUBJECTS

Approximately 22 subjects will be eligible for this study.

INCLUSION AND EXCLUSION CRITERIA

Malignant PH and PG patients will be eligible for enrollment as defined by the inclusion and exclusion criteria as follows:

Inclusion Criteria

- 1. 18 years of age or older
- 2. Histological confirmation of PH/PG
- 3. Locally advanced or metastatic disease not amenable to surgery
- 4. Patients enrolled in the main branch should have measurable disease. Patients with a predominance of bone disease who have small, non-measurable or small measurable lesions other than bone, may be included per the principal investigator's discretion, in the exploratory branch of the study for patients with bone metastases only.
- 5. Progressive disease per RECIST 1.1 as determined by the investigator within the 12 months preceding study enrollment
- 6. Assessment of all known disease sites, eg, by computerized tomography (CT) scan, magnetic resonance imaging (MRI), bone scan as appropriate, and/or FDG-PET scan within 28 days before the first dose of cabozantinib
- 7. Eastern Cooperative Oncology Group (ECOG) performance status of ≤ 2 .
- 8. Life expectancy of at least 3 months
- 9. Organ and marrow function and laboratory values as follows within 4 days prior to the first dose of cabozantinib:
 - a. Absolute neutrophil count (ANC) $\geq 1500/\text{mm}^3\text{without colony stimulating factor support}$
 - b. Platelets $\geq 100,000/\text{mm}^3$

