protein). CTx will be done, if patient has bone metastases, at screening and every 8 weeks during the first 52 weeks, then every 12 weeks.

If the subject is unable to have a study assessment taken within the defined time window due to an event outside of his or her control (eg, clinic closure, personal emergency, inclement weather, vacation), the assessment should be performed as close as possible to the required schedule.

Regular tumor assessments should be performed in accordance to the guidelines in Section 5.5 to determine if PD is present.

The Treatment Period ends when a subject receives his or her last dose of study treatment; the subject then enters the Post-Treatment Period.

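### Time to skeletal events, their incidence and CTx are defined only for the 8 bone-only patients, which leaves out about half of the trial's expected patients with bone metastases

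*Combined protocol and SAP*

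**What the plan says.** The synopsis and section 2.1 carry the same exploratory list. In the synopsis it is headed "Exploratory Endpoints (For patients with only bone metastases n=8", and in section 2.1 "Exploratory Endpoints (For patients with only bone metastases". Items 3 to 5 are "Time to skeletal related events", "Incidence of skeletal related events at 4 months and one year" and "Markers of bone turnover (bone specific alkaline phosphatase and CTx". None of the secondary endpoints, which apply to all patients, covers SREs or bone turnover.

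Section 1.3.1 sets a main branch of 14 patients with measurable disease, with or without bone metastases, and an exploratory branch of 8 with bone metastases only. It splits the disease population into 40% visceral only, 20% bone only, and "40% have visceral and bone metastases". The background (synopsis and section 1.1) gives the skeletal risk without separating these groups: "Up to eighty percent of patients with bone metastases develop skeletal related events (SREs"), with a median of 4.4 months to the first event.

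On data collection, footnote 1 of Table 5-1 says "CTx will be done, if patient has bone metastases, at screening and every 8 weeks during the first 52 weeks". Section 5.1 and footnote 4 of Table 5-1 require bone scans in patients with both visceral and bone disease.

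**The concern.** The reason given for studying skeletal events applies to anyone with bone metastases, yet the endpoints are confined to the bone-only branch. Patients with both bone and visceral disease are, by section 1.3.1, twice as common as bone-only patients (40% against 20%). They have CTx drawn, but no listed objective uses it.

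The cost is precision and applicability. Skeletal outcomes would be described in 8 patients from the less common pattern of disease, in a rare tumor at one site, when a similar or larger number with bone metastases is expected in the other branch.

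**Working it through.** **The plan's own precision figure.** Sections 2.2.1 and 7 give 95% intervals for a 45% rate. The usual formula, p ± 1.96 × √(p(1−p)/n), reproduces both:
- n = 8: 45 ± 34.5 points, or 10.5 to 79.5%, as stated.
- n = 14: 45 ± 26.1 points, or 18.9 to 71.1%, as stated.

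**Expected main-branch patients with bone metastases.** The share is (both sites) / (visceral only + both sites), multiplied by 14. This takes visceral disease to stand for measurable disease.
- Section 1.3.1 split (40/40/20): 40/(40+40) = 50%; 14 × 0.50 = 7.0.
- Section 1.1, skeleton involved in 80%, with bone-only taken as 20% of all patients: 60/(20+60) = 75%; 14 × 0.75 = 10.5.
- Section 1.1, with bone-only taken as 20% of that 80% (16%): 64/(20+64) = 76.2%; 14 × 0.762 = 10.7.

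The spread arises because the documents disagree: 80% skeletal involvement in section 1.1, but 40% + 20% = 60% in section 1.3.1. These are expected counts. The binomial 95% range is 3 to 11 of 14 at a 50% share and 7 to 13 at 75 to 76%.

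**Share left out.** Total with bone metastases is 8 + 7 = 15 to 8 + 11 = 19. Left out: 7/15 = 47% to 11/19 = 58%.

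**Precision if all were fully followed.** Exact (Clopper-Pearson) 95% intervals:

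| Patients | Incidence near 50% | Width (points) | Incidence near 75–80% | Width (points) |
|---|---|---|---|---|
| 8 | 4/8: 15.7–84.3% | 68.6 | 6/8: 34.9–96.8% | 61.9 |
| 15 | 8/15: 26.6–78.7% | 52.1 | 12/15: 51.9–95.7% | 43.8 |
| 19 | 10/19: 28.9–75.6% | 46.7 | 15/19: 54.4–93.9% | 39.5 |

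With the plan's own formula at 45%, the half-width goes from 34.5 points to 25.2 (n = 15) or 22.4 (n = 19).

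**What is collected in the main branch.**
- CTx: scheduled for any patient with bone metastases.
- Bone scans: scheduled for patients with bone and visceral disease.
- Adverse events and concomitant medications: recorded for everyone.
- SREs: no row in Table 5-1 and no definition in section 7. The background only gives examples (bone pain, fracture, cord compression) needing radiation or surgery. Section 3.4.2 lists medications, transfusions and supplements for the CRF, but does not name radiation or surgery.
- Bone specific alkaline phosphatase: in neither Table 5-1 nor the section 5.4 panel, which lists only ALP. It is scheduled for nobody.
- After the last dose: one scheduled visit at 30 to 37 days (section 5.3), with further follow-up only for treatment-related events.

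The gaps for SREs and bone specific alkaline phosphatase apply equally to the 8 bone-only patients.

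**The case against.** The strongest case is that widening the population would not by itself deliver the SRE endpoints. They have no definition and no assessment row, and scheduled follow-up ends about a month after the last dose. One-year incidence is then unobserved in anyone who stops early. Main-branch patients normally stop at progression, including visceral progression (sections 2.5 and 5.5), so the reason for censoring may differ by branch, and a pooled figure is not simply a sharper estimate of the same quantity. This stands. It is why SRE capture belongs in the fix, why results should also be shown by branch, and why the interval widths are a best case. It does not justify the restriction, because the capture gap is the same in the bone-only branch.

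Four stronger readings are tempting and are not supported:
- *The two groups face the same risk.* The documents give one SRE figure for all patients with bone metastases and never compare bone-only with mixed disease.
- *All the data are already there.* This is true for CTx and bone scans, but not for SREs or bone specific alkaline phosphatase.
- *The trial will observe 15 to 19 patients with bone metastases.* These are expected counts. Inclusion criterion 4 lets bone-predominant patients with small measurable lesions enter the exploratory branch, which could lower the main-branch count and means the 8 need not be strictly bone-only.
- *Main-branch data are thrown away.* Section 7 permits descriptive and longitudinal summaries, and adverse events are listed for all treated patients. What is missing is a stated objective and population.

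It is also fair to say that these are exploratory endpoints in a single-arm trial of about 22 patients, and that an interval 47 to 52 points wide remains descriptive.

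**Conclusion.** The point holds as a matter of population definition. The restriction leaves out about half (47 to 58%) of the expected patients with bone metastases, and CTx is collected from patients for whom no objective uses it. The gain from removing it is moderate: at best, interval width near 50% incidence falls from 68.6 points to about 52 or 47. That rests on three assumptions: the documents' disease shares apply to those enrolled, visceral disease stands for measurable disease, and follow-up is complete. The last is unlikely for one-year incidence under the current schedule. Equal risk in the two groups is neither shown nor needed, since reporting by branch lets any difference be seen. The change is worth making but is not critical, because no primary or secondary result depends on it.

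**What to change.** In section 2.1 and the synopsis, define exploratory endpoints 3 and 4 (time to SRE; SRE incidence at 4 months and one year) and the CTx part of endpoint 5 for all treated patients with bone metastases at baseline, in either branch. Report each overall and by branch. Keep endpoints 1 and 2 (FDG-PET) for the bone-only branch.

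For the SRE endpoints, write one definition, record SREs on the CRF in both branches (including radiation or surgery to bone), and estimate time to SRE and incidence by Kaplan-Meier with censoring at last contact. State the number still under observation at 4 months and one year, so that readers can see how far early stopping limits the estimate.

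The cost is a small amount of extra CRF capture and one further tabulation. No new patients or visits are needed, and the CTx extension needs no new tests. Bone specific alkaline phosphatase cannot be extended in the same way because it is not scheduled in either branch.
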